### **List of Abbreviations**

mTOR – formerly mammalian Target of Rapamycin

RAPA – rapamycin

P-gp – permeability glycoprotein

CLOX – clock drawing task

IL-6 – interleukin 6, a pro-inflammatory cytokine and an anti-inflammatory myokine

VEGF – vascular endothelial growth factor

NGF – nerve growth factor

TGF-B1 – transforming growth factor beta-1

## Study Summary

Title	Effect of Topical Rapamycin Ointment on Keloid Regression: A pilot study in human subjects
Protocol Number	HSC20190291H
Phase	Pilot
Methodology	For each participant, one keloid will be treated with topical RAPA ointment while the second keloid will serve as an untreated control. 8% RAPA ointment will be applied to the 'treatment' keloid and the second receives petrolatum-only vehicle, to allow each subject to be his/her own control.
Study Duration	7 months including screening and post treatment follow up
Study Center(s)	Audie L. Murphy VA Hospital
Objective	1. To test whether topical rapamycin regresses established keloids in humans by measuring surface area and height changes in the scar over time (6 months) 2. To test safety of product and feasibility of conduct for future clinical trial
Number of Subjects	Screen up to 20 participants to achieve 5 completers
Inclusion Criteria	1. Age 18-75 years old with at least 2 keloid scars (extant at least 1 year) in similar body locations that are easy to reach to apply ointment 2. Subjects will be in good health with all chronic diseases (hypertension, coronary artery disease, etc.) clinically stable 3. Cognitive functioning ( $\text{CLOX1} \geq 10$ and $\text{CLOX2} \geq 12$ ) sufficient to provide informed consent and be able physically to apply QD ointment to affected area 4. Able to attend monthly clinic visits for 6 months
Exclusion Criteria	1. Diagnosis of diabetes 2. Exclusionary medications: systemic steroid or immunosuppressant therapy within past 6 months or local area steroid treatment within 3 months 3. History of allergy to rapamycin or petrolatum-based products
Study Product, Dose, Route, Regimen	8% rapamycin in petrolatum ointment vs. vehicle only
Duration of administration	6 months, once daily
Statistical Methodology	Keloid surface area and height data will be analyzed using ANOVA

## 1. Introduction

This document is a protocol for a human research study. This study shall be conducted according to Good Clinical Practice guidelines as adopted by FDA, applicable government regulations, and Institutional research policies and procedures.

### 1.1. *Background*

Keloids are dermal fibroproliferative lesions induced by skin wounding and are most common in darker pigmented persons, particularly Africans, Hispanics, and Asians with up to 16% of these minority populations being at risk (17). Keloids can cause significant physical discomfort including pruritis, pain, and limitation of joint mobility; however, the worst sequelae are significant cosmetic defects and deformities. No truly effective keloid therapy exists, yet one is clearly needed. No laboratory animal models of keloids exist; instead, most work has been done on post-surgical samples with subsequent cell culture. Because keloid recurrence rate is high (up to 54% after excision) obtaining a biopsy solely for research can be considered unethical (17, 19). Based on cell culture studies, increased production of cytokines and growth factors including IL-6, VEGF, NGF, and TGF-B1 that activate of the mechanistic (formerly mammalian) Target of Rapamycin (mTOR) are mechanistically involved in keloid formation (18). As activation of mTOR is likely involved in the keloid formation, extant knowledge suggests that inhibition of mTOR activity with agents such as rapamycin would inhibit keloid development and maintenance.

### 1.2. *Innovation*

Because keloid recurrence rate is high (up to 54% after excision) obtaining a biopsy solely for research, though not often done, has revealed some pathophysiological mechanisms in keloid formation and maintenance (17, 19). Based on such cell culture studies with cells derived from human keloid biopsies, increased production of cytokines and growth factors including IL-6, VEGF, NGF, and TGF-B1 that activate of the mechanistic (formerly mammalian) Target of Rapamycin (mTOR) are mechanistically involved in keloid formation (18). Furthermore, and particularly relevant to our proposal, tissue extracts obtained from established keloid scar tissue demonstrated elevated expression of mTOR, p70KDa S6 kinase (p70S6K), and increased levels of their activated forms, suggesting roles in already extant keloid scars (14). Given that many mechanisms implicated in keloid development involve activation of mTOR, mTOR inhibition has been suggested as a potential therapeutic approach to preventing keloids (14, 20, 21). In addition, findings that established keloid scars contain elevated expression of mTOR, p70KDa S6 kinase (p70S6K), and their activated forms, mTOR inhibition may facilitate treatment of already extant keloids (14). Rapamycin (RAPA) is an FDA approved mTOR antagonist. Work in our laboratory established that this agent could be delivered transdermally as an ointment without producing measurable levels in the circulation and with no systemic effects. Subsequent serendipitous work in our laboratory suggested that application of topical RAPA ointment regressed established keloids, again without systemic effects. We will test this innovative topical treatment in persons susceptible to keloids who have established keloid scars that have not received any prior treatment.

The number of diagnosed keloids is increasing as decorative piercing is increasingly practiced, especially in visible anatomical sites and in younger age groups. Patients suffering from visible keloids may be affected by their disfigurement and suffer psychological consequences. Indeed, the quality of life can be severely impaired (40). There is no single effective therapeutic treatment for keloids. Numerous treatments have been described including occlusive dressings, compression therapy, steroid injections, imiquimod cream, laser therapy, surgical excision, cryosurgery, 5-fluorouracil, bleomycin, interferon therapy, and even radiation treatments (31). Unfortunately, these treatments are ineffective long-term and post-treatment recurrence is common (8, 40). A simple, effective, and safe treatment is needed.

#### **1.4. Investigational Agent**

Rapamycin (RAPA) concentration of 8% RAPA in a petrolatum vehicle will be compounded and supplied by Doyle's Pharmacy (Houston, TX). We will have subjects self-administer study product or placebo to be applied directly to each treatment keloid. This schedule replicates that which generated our preliminary keloid-regressing results. Our placebo control ointment will be the petrolatum vehicle only. Both ointments will have the same consistency and smell.

#### **1.5. Dose Rationale and Risk/Benefits**

Our pilot trial will use 0.5-1.0ml applications of 8% RAPA in a petrolatum vehicle to established keloid lesions in 5 persons with at least 2 chronic keloids greater than 1-year duration in similar body regions. In preliminary studies, we found that applying this 8% RAPA ointment reliably produced local transdermal delivery of RAPA without producing any measurable RAPA levels in systemic blood (6). Treatment will be applied once daily for 6 months. Surface areas of keloids will be monitored monthly and compared over time to evaluate responses.

Topical RAPA Ointment: RAPA from LC Labs was used in our preliminary studies (7, 11). Initially, we used a formulation of 1% RAPA in a petrolatum vehicle (6). This topical preparation had been demonstrated to regress skin angiofibromas in tuberous sclerosis patients (6). No systemic RAPA blood levels, alterations in complete blood counts, changes in complete metabolic profiles, or skin irritation occurred in the tuberous sclerosis patients in that study (6). An alternative topical formulation of RAPA in a vehicle of either 50:40:10 capric acid/isopropyl myristate/benzoyl alcohol or 50:50 capric acid/benzoyl alcohol has also been tested in humans (15). The latter formulations, in up to 8% RAPA concentrations, improved psoriasis, was undetectable in blood, and produced no clinical blood test changes; however, a few participants had adverse reactions to the vehicle. Because topical 1% RAPA in petrolatum was documented to exert local effects without any systemic effects or adverse reactions to the vehicle, we chose this formulation and strength for our initial studies. We assessed transdermal delivery by applying the 1% RAPA ointment over an intradermal  $\mu\text{D}$  probe and sampled RAPA delivery into the cutaneous interstitial space. We found 1% RAPA produced measurable interstitial RAPA concentrations in some, but not all cases. We therefore increased the RAPA concentration in petrolatum to 8% and repeated our  $\mu\text{D}$  measurements. We found that we could reliably achieve an interstitial level of  $11.47 \pm 4.03 \text{ ng/ml}$  RAPA with this 8% RAPA ointment that was chosen for further studies. This 8% RAPA formulation subsequently prevented keloid formation at a skin biopsy site and regressed an established keloid in a keloid-prone subject leading to the present pilot proposal.

One keloid will be treated with topical RAPA while the second keloid will serve as an untreated control by receiving petrolatum vehicle only. 8% RAPA ointment will be applied to the 'treatment' keloid but not the second, to allow each subject to be his/her own control.

**Potential Risks:** In a randomized, double blind, vehicle-controlled multicenter study of 179 patients with facial angiofibromas secondary to tuberous sclerosis complex, 59 enrolled and randomized to 1% RAPA, 63 to 0.1% RAPA, and 57 to the vehicle-only group (23). Topical rapamycin was generally well-tolerated, with no measurable systemic absorption. Nearly all AEs were mild, with no drug-related moderate, severe, or serious events.

Apparent drug-related adverse effects at the application site were limited to 10% or less incidence for:

- Discomfort or pain
- Pruritis
- Acne
- Erythema
- Irritation

In this same trial, generalized symptoms occurred in a few subjects, including nasopharyngitis, nasal congestion, sinusitis, application site papules and applications site paresthesia. There were no reports of generalized symptoms such as pruritis, nausea, mouth ulceration or cough.

## 2. Study Objective

We will test the primary hypothesis that treatment of extant keloids with 8% topical RAPA ointment will regress keloid surface area and height.

Finally, to assess safety, we will gather data on anticipated common side effects of the medication, including any adverse drug reactions other than those listed as potential risks in Section 1.5 above.

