## 3. Study Design

### **3.1. Subjects**

We will screen up to 20 persons ages 18-75 without diabetes or unstable, chronic diagnoses. We intend to complete 5 subjects achieving 6 months of treatment with topical RAPA. Refer to Section 4, Inclusion/Exclusion Criteria.

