## 7. Statistical Plan

### 7.1. Statistical Methods

For all analyses, the statistical threshold for significance will be set at  $p<0.05$ .

Keloid surface area and height data will be analyzed using ANOVA for repeated measurements using a

model similar to that described for the analysis of the preliminary data (see INNOVATION, above) with the addition of a random effect for subject (47). This analysis can be modified to include between-subject factors if such factors (sex, race, etc.) are identified for investigation.

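### With five within-patient pairs, resting efficacy on p<0.05 is likely to be uninformative and can mislead; plan a RAPA-minus-vehicle estimate with a confidence interval

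*Combined protocol and SAP*

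**What the plan says.** The Study Summary subtitles the trial "A pilot study in human subjects" and sets its size as "Screen up to 20 participants to achieve 5 completers". Section 3.1 repeats the target: "We intend to complete 5 subjects achieving 6 months of treatment with topical RAPA". Each participant has one keloid on 8% RAPA and one on vehicle, "to allow each subject to be his/her own control" (Section 1.5).

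The efficacy aims are worded as tests in the Study Summary, in the Section 2 hypothesis ("We will test the primary hypothesis that treatment of extant keloids with 8% topical RAPA ointment will regress keloid surface area and height") and in two of the three objectives listed there. Section 7.1 is the whole statistical plan. It opens: "For all analyses, the statistical threshold for significance will be set at" p<0.05. It continues: "Keloid surface area and height data will be analyzed using ANOVA for repeated measurements using a" model like the one used for the preliminary data, plus a random effect for subject. Area and height are measured before treatment and then monthly (Section 3.2).

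The visible text gives no sidedness, error term, effect size, SD, power or confidence interval. The photography and caliper analysis text in Section 6.1 defines percentage flattening for a keloid, but no contrast between the two keloids. The Study Summary adds a safety and feasibility objective, with no numerical criterion.

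**The concern.** The Study Summary says that the pilot serves a future trial. That trial will need a plausible range for the effect and the spread of the within-patient difference. A significance threshold supplies neither. If a useful effect is reported only as not significant, it may be dropped. If an estimate is carried forward because it crossed p<0.05, it will tend to be too large, and the next trial too small. A further risk is that six monthly readings on the same keloid are treated as independent evidence about treatment.

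**Working it through.** There is no sample-size or power figure in the documents to reproduce. The inputs taken from them are n = 5 pairs, alpha = 0.05, and one baseline plus six monthly readings per keloid. Effect sizes and variance ratios below are assumptions. SD means the SD of the within-patient differences, except in step 5.

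**1. Exact paired tests (sign, Wilcoxon signed-rank, sign-flip).** Five pairs give 2^5 = 32 sign patterns.
- Smallest two-sided p = 2/32 = 0.0625.
- Smallest one-sided p = 1/32 = 0.031, reached only if all five pairs favour RAPA.

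**2. Paired t on one difference per patient (4 df).** The smallest significant observed effect is t/√n.
- Two-sided: 2.776/√5 = 1.24 SD. This is also the half-width of the 95% interval.
- One-sided: 2.132/√5 = 0.95 SD.

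**3. Power of that t test (noncentral t, 4 df, noncentrality = true effect × √5).**

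| True effect (SD) | Two-sided | One-sided |
|---|---|---|
| 0.5 | 14% | 24% |
| 0.8 | 28% | 44% |
| 1.0 | 40% | 58% |
| 1.5 | 71% | 86% |
| 2.0 | 91% | 97.5% |

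Reaching 80% power needs a true effect of 1.68 SD two-sided or 1.36 SD one-sided.

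**4. Overstatement among significant two-sided results (400,000 simulated five-pair trials per effect).** On average it is 2.0-fold at a true 0.5 SD, 1.5-fold at 0.8, 1.3-fold at 1.0, 1.10-fold at 1.5 and 1.03-fold at 2.0.

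**5. The ANOVA of Section 7.1, with subject as the only random effect.** Six post-baseline visits give 5 × 2 × 6 = 60 readings. Removing 12 treatment-by-visit means and 4 subject df leaves 60 − 12 − 4 = 44 residual df, so the 4-df limit in step 2 does not apply. Set the visit-error variance to 1 and the between-keloid variance within a subject to k². With no treatment effect:
- the expected treatment mean square is 1 + 6k²;
- only 4 of the 44 residual df carry the keloid term, so the expected residual mean square is 1 + 6k² × 4/44.

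The ratio of the two should be 1.
- k = 0: ratio 1.
- k = 0.5: 2.5/1.136 = 2.2.
- k = 1.0: 7/1.545 = 4.5.

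The critical F(1, 44) is 4.06. Dividing it by these ratios gives 4.06, 1.85 and 0.90, with upper-tail probabilities of about 5%, 18% and 35%. A null simulation of 5,000 trials per setting gave 4.9%, 18% and 35%. In it, the paired t on subject means stayed near 5%, and 53%, 78% and 86% of the ANOVA rejections had an observed paired effect below 1.24 SD.

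**The case against.** The strongest objection is that steps 1 to 3 describe tests the protocol does not plan. Section 7.1 names neither an exact test nor a paired t. This stands. A reader might infer that the planned analysis cannot reach p<0.05 below 1.24 SD; step 5 shows that, as literally worded, it can. Its main hazard is false positives from an unspecified error term, rather than low power.

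A reader might also infer that no exact paired test could ever be significant. That holds only two-sided. Section 7.1 states no sidedness and the hypothesis is directional, so a one-sided exact p of 0.031 is possible.

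Large effects cannot be excluded either. The documents give no SD, and their only clinical signals are one treated biopsy site that formed no keloid and one lesion that regressed. At 1.5 to 2.0 SD, a paired t has reasonable power and little overstatement.

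The model itself may be better specified than it appears. Section 7.1 refers back to the preliminary-data analysis. The visible Section 1.2 does not describe it, and part of Section 1.3 was not available for this review. A keloid-level error term, if given there, would remove the inflation in step 5, but it would not create five more patients.

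Finally, a 4-df t interval rests on the same normality assumption as the t test and excludes zero exactly when the two-sided t gives p<0.05. That is true. The gain lies in reporting the effect range and spread, with one value per patient, instead of a verdict.

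**Conclusion.** The point holds in a limited form. A p-value from five pairs is likely to be uninformative and can mislead, and the visible plan offers no between-keloid estimate with an interval in its place. If analysed as one difference per patient, two-sided power is at most 40% for true effects up to 1.0 SD. If analysed by the literal subject-only ANOVA, type I error is about 5% with no between-keloid variation, rising to 18% and 35% at between-keloid SDs of 0.5 and 1.0 visit-error SDs. These figures assume normal data and the stated effect sizes and variance ratios, none of which the documents supply.

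Two stronger readings are not supported. The test cannot be said to mislead whatever happens: a two-sided paired t holds its 5% level under normality and detects very large effects. Nor is p<0.05 a declared success criterion: Section 7.1 calls it a significance threshold, no go/no-go decision is tied to it, and safety and feasibility are a separate objective. This is a change the team should make, not a fatal flaw.

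**What to change.** In the Study Summary, Section 2 and Section 7.1:
- Define the primary result, separately for area and for height, as the mean within-patient RAPA-minus-vehicle difference in change from baseline to Month 6. Report it with a 95% t interval (4 df with five pairs), the SD of the paired differences, and a plot or listing of all individual pairs.
- Keep the monthly data as a descriptive secondary analysis.
- Label any p-value descriptive, and state that neither p<0.05 nor p≥0.05 alone supports an efficacy conclusion.
- Keep the sample size.

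Using one value per patient also closes the route by which repeated visits inflate significance. The cost is wording in three places, with no added patients, visits or measurements. The team gives up a claim of statistical significance. The t interval still assumes approximate normality, which five pairs cannot verify; that is why the individual values must be shown.

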### **Objectives:**

1. To compare the effect of topical RAPA 8% ointment to treat established keloid versus untreated keloid
2. To test whether regression of surface area occurs after 6 months of treatment
3. To test whether regression of height of treated keloid occurs after 6 months

## 3. Study Design

### **3.1. Subjects**

We will screen up to 20 persons ages 18-75 without diabetes or unstable, chronic diagnoses. We intend to complete 5 subjects achieving 6 months of treatment with topical RAPA. Refer to Section 4, Inclusion/Exclusion Criteria.

### **3.2. General Design**

Our pilot trial will use daily 0.5-1.0ml applications of 8% RAPA in a petrolatum vehicle to treat established keloid lesions in 5 persons with at least 2 chronic keloids in similar body regions (greater than 1-year duration). Treatment will be applied once daily for 6 months. One keloid will receive 8% RAPA ointment and the other keloid will receive petrolatum-only ointment as a control. Surface areas and height of keloids will be monitored pre- and post-treatment to evaluate responses.

We will measure keloid surface area and height changes pre-treatment and thereafter on a monthly basis using standardized digital photography with a tripod-mounted 8MP Canon S5is camera and calipers to measure keloid height (37).

Surface areas of all photographed lesions will be measured with Image J (<http://rsbweb.nih.gov/ij/index.html>), a public image-processing program that we used to analyze our preliminary data and will use the same approach in this study.

### 3.3. Study Endpoints

#### Primary outcome:

- Change in keloid surface area and keloid height

### 3.4. Potential Risks to Subject Safety

#### 3.4.1. Drug Administration.

The most common side effects of rapamycin include:

TOPICAL:	SYSTEMIC: (≥ 20%)		
• Discomfort or pain	• Stomatitis	• Acne	• Dizziness
• Pruritis	• Diarrhea	• Chest pain	• Myalgia
• Erythema	• Abdominal pain	• Peripheral	• Hypercholesterolemia
• Irritation	• Nausea	• URI	
• Rash	• Nasopharyngitis	• Headache	

**3.4.2. Blood withdrawal.** Subjects will undergo venipuncture to obtain blood specimen for complete blood count (CBC) and comprehensive chemistry (CMP) for general safety purposes. Although our research staff are experienced in venipuncture and aseptic technique, the most common risks to phlebotomy include mild pain from the needlestick or venous catheter, bleeding, bruising, and rarely infection.

**3.4.3. Psychosocial.** Subjects may experience psychological distress from assessments of cognitive function (CLOX), which will be minimized with use of privacy barriers.

## 4. Subject Selection and Withdrawal

#### 4.1. Inclusion Criteria

- Both sexes of ages 18-75 years in good general health
- All ethnic groups regardless of Veteran status
- Must have at least two (2) keloids present for at least 1 year, located in a similar body area that can be easily reached, and be willing to self-administer investigational ointment and placebo control
- Cognitive functioning (CLOX1  $\geq$ 10 and CLOX2  $\geq$ 12 ) sufficient to provide informed consent and be able physically to apply QD ointment to affected area
- Negative pregnancy test

#### 4.2. Exclusion Criteria

- Diagnosis of active or chronic skin disorders
- History of, or active treatment for local or systemic infections, especially of skin

- Current treatment with systemic steroid or immunosuppressant therapy within the past 6 months or local steroid treatment within 3 months. Potential subjects may be re-screened if local treatment is discontinued for the 3-month period.
- Active/unstable conditions: inflammatory, thyroid, autoimmune, gastrointestinal (GI), hematologic, or neoplastic disorders. Subjects with clinical lab values outside the normal range and determined to be clinically significant by investigator will be excluded.
- Subject is considered unsuitable for the study in the opinion of the investigator for any other reason

#### **4.3. Subject Recruitment and Screening**

Subjects will be recruited and by referral from any Audie L. Murphy VA Hospital outpatient clinic or research unit, through medical record review, and by referral from dermatology and other outpatient clinics at UT Health San Antonio. Fliers and other means of advertisement may be distributed per applicable institutional policy.

Screening will be performed following consent at Visit 1, prior to baseline data collection and assessment of eligibility criteria listed above.

